The purpose of this study is to evaluate the ADAPT (Adaptive Positioning Technology, Stryker®, USA) computer navigation platform in a controlled, randomized fashion to determine its effect on TAD, lag screw cut-out, operative time, fluoroscopy time and number of Kirschner wire (K wire) passes prior to insertion of the final implanted device. Additionally, 1 year follow-up will compare postoperative complications, mobility, range of motion, social dependency and pain level between procedures that utilized the ADAPT platform and those that did not.

Study Design: This will be a prospective, randomized, double-blind, controlled trial with two treatment cohorts. Cohort 1 will consist of 30 patients with closed peritrochanteric femur fractures who undergo open reduction internal fixation with a Stryker© Gamma intramedullary nail using traditional fluoroscopy for insertion of the lag screw (control group). Cohort 2 will consist of 30 patients with closed peritrochanteric femur fractures who undergo open reduction internal fixation with a Stryker© Gamma intramedullary nail using the Stryker© ADAPT platform to assist with insertion of the lag screw (treatment group). Patients will be blinded to treatment group allocation as will clinicians/researchers during data processing/analysis. The primary outcome will be TAD, as measured on AP and lateral hip radiographs. Secondary outcomes will be position of the lag screw as described by Cleveland et al, operative time, fluoroscopy time, and number of K wire passes prior to final placement of the lag screw. Additionally, evidence of lag screw cut-out on hip radiographs, hip range of motion relative to the contralateral hip, mobility and social dependency as defined by the Harris Hip Score, and pain level (visual analog scale) will be assessed at 3 month, 6 month, 1 year, and 2 year follow up visits.

Statistical Procedures: Descriptive statistics will be calculated to compare patient demographics between the two cohorts. The Student t-test and the Fisher's exact test will be used to compare outcomes between the two cohorts. Based on a previous study by Herzog et al (2019), we expect the ADAPT platform to lead to an average reduction in TAD of 8 mm (24.9 mm +/- 6.68 mm without ADAPT vs. 16.9 mm +/- 6.30 mm with ADAPT). Accordingly, in order to achieve a power of 0.8 with an alpha of 0.05 and a beta of 0.2, we will need to accrue 11 patients per cohort. Our plan is to enroll 30 patients per cohort.

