RESEARCH AIMS & ABSTRACTS

Research Question(s)/Hypothesis(es): We hypothesize that use of the ADAPTTM platform will lead to a lower mean TAD and a greater proportion of patients with a TAD of 25 mm or less. We do not expect a difference in the proportion of patients with optimal lag-screw position within the femoral head as defined by Cleveland et al. Use of the ADAPT platform will lead to no difference in operative time or blood loss, decreased fluoroscopy use, and fewer K wire passes. In terms of radiographic evidence of screw cut-out, we expect no difference at any

of the follow up visit time points. Additionally, we expect no difference in hip range of motion, mobility and social dependency as defined by the Harris Hip Score, or pain level at any of the follow up visit time points.

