Scientific Abstract: Peritrochanteric femur fractures are the most common type of fracture requiring orthopaedic surgical intervention. Successful treatment with cephalomedullary nail fixation can restore patients' baseline ambulatory function and prevent complications associated with prolonged bedrest and immobilization. However, failure of fixation due to lag screw cut-out has an incidence rate of nearly 8% following open reduction internal fixation with a cephalomedullary nail. Previous research has identified the tip-apex distance (TAD) of the lag screw as the strongest predictor of lag screw cutout. Accordingly, computer navigation platforms have been developed to reliably achieve a TAD of less than 25 mm. To date, however, only one clinical study has compared computer navigation to traditional fluoroscopy in achieving a TAD of less than 25 mm. While this study demonstrated significantly improved accuracy of lag screw placement in the computer navigation cohort with no significant effect on average operating time, the study did not assess other important intraoperative variables nor postoperative outcomes. The purpose of this study is to determine if computer navigated lag screw placement during cephalomedullary nail fixation utilizing the novel ADAPT platform will lead to a lower mean TAD and a greater proportion of patients with a TAD of 25 mm or less. This will be a prospective, randomized, single-blinded, controlled trial with two treatment cohorts. Cohort 1 will consist of patients with closed peritrochanteric femur fractures who undergo open reduction internal fixation with a Stryker[©] Gamma cephalomedullary nail using traditional fluoroscopy for insertion of the lag screw. Cohort 2 will consist of patients with closed peritrochanteric femur fractures who undergo open reduction internal fixation with a Stryker[©] Gamma cephalomedullary nail using the Stryker[©] ADAPT platform to assist with insertion of the lag screw. Patients will be blinded to treatment group allocation but clinicians/researchers will not. The primary outcome will be TAD as measured on postoperative AP and lateral hip radiographs. Secondary outcomes will be position of the lag screw as described by Cleveland et al, operative time, fluoroscopy time, and number of K wire passes prior to final placement of the lag screw. Additionally, evidence of lag screw cut-out on postoperative hip radiographs, hip range of motion relative to the contralateral hip, mobility and social dependency as defined by the Harris Hip Score, and pain level will be assessed at 3 month, 6 month, 1 year, and 2 year follow up

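### Do the unlisted blood loss and complication outcomes, and the 1-year versus 2-year wording, leave stated questions unanswerable?

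*Combined protocol and SAP*

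**What the plan says.** Under Research Question(s)/Hypothesis(es), the plan expects that "Use of the ADAPT platform will lead to no difference in operative time or blood loss, decreased fluoroscopy use, and fewer K wire passes". This is the only mention of blood loss in the document.

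The purpose paragraph of the Background says the trial will "determine its effect on TAD, lag screw cut-out, operative time, fluoroscopy time and number of Kirschner wire (K wire) passes". It continues: "Additionally, 1 year follow-up will compare postoperative complications, mobility, range of motion, social dependency and pain level". That sentence is the only place where complications as a group are to be compared.

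Study Design then sets out the outcomes. The primary is TAD: "The primary outcome will be TAD, as measured on AP and lateral hip radiographs". The secondaries are Cleveland screw position and "operative time, fluoroscopy time, and number of K wire passes prior to final placement of the lag screw". For follow-up it adds "Additionally, evidence of lag screw cut-out on hip radiographs, hip range of motion relative to the contralateral hip", Harris Hip Score items and pain, which "will be assessed at 3 month, 6 month, 1 year, and 2 year follow up visits". The Scientific Abstract repeats the same lists ("Additionally, evidence of lag screw cut-out on postoperative hip radiographs, hip range of motion relative to the contralateral hip" and so on), and the lay abstract gives the same four visits.

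**The concern.** Three statements do not line up. Blood loss carries a hypothesis but is not an outcome. Complications are promised as a comparison but are not an outcome, apart from cut-out, which the purpose paragraph names separately. The purpose paragraph speaks of 1 year while the visit schedule ends at 2 years.

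If the outcome lists alone decided what is recorded, blood loss and the remaining complications might not be captured, and a blood-loss figure not noted at surgery could be hard to rebuild. With two horizons in the text, a reader may also fear that the reported time point could be picked once the results are known. The trial's rationale adds weight: it justifies itself partly by intraoperative and postoperative outcomes that the earlier study left out, and the two unlisted items belong to that territory.

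**Working it through.** **Step 1: hypotheses against outcome lists.** Items come from Research Question(s)/Hypothesis(es); outcomes come from Study Design and the Scientific Abstract.

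| Hypothesised item | Listed outcome |
|---|---|
| Mean TAD | Primary |
| Proportion with TAD at or under 25 mm | Derived from the primary |
| Cleveland screw position | Secondary |
| Operative time | Secondary |
| Blood loss | None |
| Fluoroscopy use | Secondary (time) |
| K wire passes | Secondary |
| Cut-out | Follow-up |
| Range of motion | Follow-up |
| Mobility and social dependency | Follow-up (Harris Hip Score) |
| Pain | Follow-up |

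Ten of 11 match.

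**Step 2: purpose paragraph against outcome lists.** It names five items for effect (TAD, cut-out, operative time, fluoroscopy time, K wire passes) and five for follow-up (complications, mobility, range of motion, social dependency, pain). Nine of the ten have a listed outcome. The tenth, complications, is covered only as far as cut-out goes.

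**Step 3: the follow-up horizon.** Visits are at 3, 6, 12 and 24 months, so a 12-month comparison is contained in the schedule. Mobility, range of motion, social dependency and pain are all assessed at that visit, so the comparison in the purpose sentence can be made as written. The hypotheses name no single visit; they cover every visit and expect no difference at any of them. Four follow-up outcomes (cut-out, range of motion, Harris Hip Score, pain) at four visits give 4 × 4 = 16 comparisons. That count is the same with or without the 1-year phrase.

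**Step 4: does the sample size depend on these items?** Inputs from Statistical Procedures: difference 8 mm, SDs 6.68 and 6.30 mm, alpha 0.05, power 0.8. Two-sided testing is assumed, since sidedness is not stated.

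- Pooled SD = √((6.68² + 6.30²)/2) = √42.156 = 6.49 mm.
- n per cohort = 2 × (1.960 + 0.842)² × 42.156 / 8² = 10.3, rounded up to 11. This is the plan's figure.
- Power by the same formula is 0.824 at 11 and 0.998 at the planned 30. A noncentral t calculation gives 0.785 at 11 and 0.822 at 12, so it would ask for 12, still far below 30.

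Only TAD enters the calculation. Listing or removing the two items would leave it unchanged.

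**Step 5: what listing them would buy at 30 per cohort.**

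- Blood loss, t-test: the 95% confidence interval half-width is t(0.975, 58 df) × √(2/30) = 2.00 × 0.258 = 0.52 SD. The difference detectable with 80% power is 0.74 SD.
- Complications, Fisher's exact test: taking the Background's cut-out rate of nearly 8% as an illustrative control rate, power is 0.029 against 0%, 0.017 against 2% and 0.010 against 4%. The comparison rates are assumptions.

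Both items would be reported descriptively whether or not they appear in a list.

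**The case for a change.** The best case for a change is that these lists are the only outcome specification in the document. Blood loss is the one hypothesised item without an outcome, which points to an oversight. Cut-out does not stand in for complications in general, because the purpose paragraph mentions it separately. Neither item has a definition, a source or a time window, and no main follow-up visit is named.

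As a description of the text, all of that stands. It does not show harm:

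- Loss of data follows only if the outcome lists alone govern collection. The document includes no data form or collection schedule, so this is an assumption. The aims themselves commit the trial to comparing both items.
- If blood loss and complications are in routine operative and clinic records, they can be retrieved. If they are not, the repair is no longer just a matter of wording. The document does not say which holds.
- The worry about choosing a time point is weak, because every visit is declared in advance with an expectation of no difference. What remains is the lack of a lead visit among non-primary outcomes. That exists regardless of the 1-year phrase, and naming one would be a preference.

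**Conclusion.** No change to the plan is needed. Two non-primary items, blood loss and complications other than cut-out, appear in the aims but not in the outcome lists: 1 of 11 hypothesised items and, in part, 1 of 10 items in the purpose paragraph. The 1-year phrase is loose wording, since that visit is one of the four scheduled. It leaves the main follow-up visit unstated but prevents no comparison.

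This is missing detail that analysts can fill sensibly: report blood loss and complications descriptively as the aims announce, and present the follow-up outcomes at each visit. No stated rule, number or analysis gives a wrong result. TAD, its test and the sample size (11 needed, 30 planned per cohort) are unaffected. Aligning the lists when the document is next revised would be reasonable housekeeping, but no conclusion depends on it.

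The judgement assumes that the team records what its own aims say it will compare. The document neither confirms nor contradicts this.

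### The plan contradicts itself on whether clinicians and researchers are blinded, and never says who reads the primary outcome (TAD) or whether that reader is masked

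*Combined protocol and SAP*

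**What the plan says.** Two sections of the combined protocol and SAP describe the blinding.

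- **Background, Study Design:** "This will be a prospective, randomized, double-blind, controlled trial with two treatment cohorts". On who is blinded: "Patients will be blinded to treatment group allocation as will clinicians/researchers during data processing/analysis".
- **Research Aims & Abstracts, Scientific Abstract:** "This will be a prospective, randomized, single-blinded, controlled trial with two treatment cohorts". On who is blinded: "Patients will be blinded to treatment group allocation but clinicians/researchers will not".

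The primary outcome is described in the same two places. Study Design has: "The primary outcome will be TAD, as measured on AP and lateral hip radiographs". The Scientific Abstract has: "The primary outcome will be TAD as measured on postoperative AP and lateral hip radiographs". The lay summary says only that films taken after surgery will be used to compare position between the groups. No section names the reader, gives the number of readers, or says whether the reader is independent of the operating surgeon or masked to allocation.

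The Research Question(s)/Hypothesis(es) paragraph states a direction for TAD: ADAPT "will lead to a lower mean TAD and a greater proportion of patients with a TAD of 25 mm or less". For lag-screw position and for cut-out it expects no difference.

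**The concern.** The two sections differ in the label for the whole trial and in whether clinicians and researchers are blinded when data are processed and analysed. Staff cannot follow both as written, and each supports a different blinding statement in the trial report.

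The primary outcome falls in the gap between them. TAD is the sum of two distances that a person measures on two views. Blinding the patient does nothing to protect that measurement; only masking the reader does. If the reader knows the arm, the readings could drift towards the stated hypothesis, both for mean TAD and for the proportion at 25 mm or less. No direction of bias is claimed for cut-out or lag-screw position, where the plan expects no difference. Masking those readings simply protects the comparison.

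**Working it through.** **1. The two sections side by side**

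| | Study Design | Scientific Abstract |
|---|---|---|
| Label | double-blind | single-blinded |
| Patients | blinded | blinded |
| Clinicians/researchers | blinded during data processing and analysis | not blinded, no stage excepted |
| TAD reader | not named | not named |
| Masking of TAD reader | not stated | not stated |

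Study Design does not claim that surgeons are blinded during the operation, so the direct conflict is over the processing and analysis stage and over the label. There are two readings of data processing in Study Design:

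- If it includes measuring the films, Study Design provides masked reading and the Scientific Abstract removes it.
- If it does not, neither section provides it.

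On neither reading does the document as a whole secure masked measurement of TAD.

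**2. The plan's own figure**

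Inputs from Statistical Procedures: means 24.9 and 16.9 mm, SDs 6.68 and 6.30 mm, alpha 0.05, power 0.80, 30 enrolled per arm. Sidedness is not stated; two-sided is assumed here.

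- SD = √((6.68² + 6.30²)/2) = √((44.62 + 39.69)/2) = 6.493 mm.
- n per arm = 2 × (1.960 + 0.842)² × 6.493² / 8² ≈ 10.3, rounded up to 11. The stated 11 per cohort reproduces by the normal approximation (the t-test gives 11.39, so 12). It is not in dispute.
- Power for 8 mm at 30 per arm (noncentral t) = 99.7%.

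**3. Mean TAD, assumed reading shift**

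The documents give no reader error, so every shift below is an assumption. The standard error of the difference is 6.493 × √(2/30) = 1.676 mm, and the noncentrality is shift/1.676. With no true effect and a two-sided 5% t-test on 58 degrees of freedom:

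| Assumed shift (mm) | Noncentrality | Rejection rate |
|---|---|---|
| 0.5 | 0.30 | 6.0% |
| 1 | 0.60 | 9.0% |
| 2 | 1.19 | 21.7% |
| 3 | 1.79 | 42.1% |

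If the 8 mm effect is real, the harm is to the estimate: 1/8 = 12.5%, 2/8 = 25%, 3/8 = 37.5%.

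**4. Proportion at 25 mm or less**

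TAD is assumed normal. Fisher's exact test is assumed for this proportion, as one of the two tests that the plan names.

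*No true effect*, both arms with mean 24.9 and SD 6.68. The true share is Φ((25 − 24.9)/6.68) = 50.6%. Reading the ADAPT arm lower by a shift s gives Φ((25 + s − 24.9)/6.68). The rejection rate is the exact binomial probability, at 30 per arm, of outcomes with two-sided Fisher p at or below 0.05.

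| Shift s (mm) | Share read as 25 mm or less | False gain (points) | Fisher rejection |
|---|---|---|---|
| 0 | 50.6% | 0 | 2.7% |
| 1 | 56.5% | 5.9 | 4.4% |
| 2 | 62.3% | 11.7 | 9.7% |
| 3 | 67.9% | 17.3 | 19.3% |

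*Planned effect true*, ADAPT arm with mean 16.9 and SD 6.30. The true share is Φ((25 − 16.9)/6.30) = 90.1%. Shifts of 1, 2 and 3 mm give 92.6%, 94.6% and 96.1%, a false gain of about 2.5, 4.5 and 6 points.

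**The case against.** The best reply has four parts.

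1. **The conflict may be mostly one of labels.** The Scientific Abstract can be taken as shorthand that those giving care know the arm, with Study Design adding blinding at the later stage. This narrows the conflict but does not remove it. The Scientific Abstract names no stage and makes no exception, and the two labels still disagree.
2. **Masked reading may already be intended**, since data processing can reasonably include measuring films. That is possible, but Study Design does not say so and the Scientific Abstract as written rules it out. An intention that must be inferred does not bind whoever reads the films.
3. **The size of the bias is assumed.** This stands. TAD is a defined distance in millimetres, and nothing in the documents shows that a systematic shift of 2 or 3 mm between arms is likely. The no-effect case for the 25 mm cut-off is also close to the worst case, because a mean of 24.9 mm sits almost on the cut-off; under the planned ADAPT values the distortion is roughly a third to two-fifths as large. At the planned effect the primary test is barely touched.
4. **The remedy asks for more than the minimum.** Reconciling the sections and stating who reads TAD, and whether masked, would cure the contradiction and the silence. Random film order and a lock on readings are good practice that makes the masking effective; they add little burden.

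**Conclusion.** The concern holds. The contradiction and the silence about the TAD reader are both in current text and depend on no calculation. Following the Scientific Abstract as written allows the primary outcome to be measured by someone who knows the arm, under a hypothesis that names the favoured direction.

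The possible harm depends on the truth. With no real effect, an assumed shift of 1 to 3 mm would raise the false-positive rate for mean TAD from 5% to between 9% and 42%. With the planned 8 mm effect, the conclusion would almost certainly stand, but its size would be wrong by 12.5% to 37.5% of 8 mm. These figures rest on assumed shifts, SD 6.493 mm, 30 analysed patients per arm and two-sided testing. The sample size is unaffected.

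This must be fixed before films are read: readings made with knowledge of the arm can be repeated but not undone.

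**What to change.** Make Study Design and the Scientific Abstract say the same thing:

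- Patients are blinded; the operating surgeon is not.
- TAD, lag-screw position and cut-out are read by study researchers from de-identified postoperative films, labelled by study ID and presented in random order.
- Allocation is withheld from readers until the readings are locked, and the analysis is still run blinded, as Study Design already provides.
- Both existing labels are replaced by one description: patient-blinded, with masked reading of radiographic outcomes and blinded analysis.
- No blinding is claimed for operative time, fluoroscopy time or K wire passes. It is claimed for range of motion and the Harris Hip Score only if their assessor is stated to be masked.

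The cost is protocol wording and relabelling of image files, with no extra imaging or patients. One constraint follows: a researcher who assisted at an operation should not read that patient's films. This assumes that the team includes someone who was not at that operation; the documents do not give the team's size.

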
visits. Student t-test and Fisher's exact test will be used to compare outcomes between the two cohorts.

Hip fractures are common injuries in which the top part of the femur bone breaks. These fractures often require surgery and are frequently treated with a metal rod that goes inside the femur, known as a cephalomedullary nail. Successful treatment of hip fractures with a cephalomedullary nail can allow patients to start walking soon after surgery. However, the cephalomedullary nail must be inserted into the correct position in the femur, otherwise it may not work properly. Traditionally, surgeons use x-rays in the operating room to determine if a cephalomedullary nail is in the correct position within the femur. Recently, however, computer navigation technology has been developed to help surgeons correctly position cephalomedullary nail devices. To date, only one study has compared x-rays to computer navigation technology in the treatment of hip fractures. While this study demonstrated more accurate placement of the cephalomedullary nail with computer navigation, the study did not consider other important outcomes such as radiation exposure, hip function and pain after surgery. The purpose of this study is to further compare x-rays and computer navigation (the ADAPT platform) for the placement of a cephalomedullary nail when treating hip fractures. This study will have two groups: group 1 will consist of patients with hip fractures who undergo surgery with a cephalomedullary nail using only x-rays, and group 2 will consist of patients with hip fractures who also undergo surgery with a cephalomedullary nail but using computer navigation (the ADAPT platform) as well as x-rays. X-rays taken after surgery will be used to compare the average position of the cephalomedullary nail in the femur between the two groups. Other variables will also be compared between the two groups including the average time required to perform the surgery, the average number of x-rays taken during the surgery, the average number of attempts required to position the cephalomedullary nail, as well as the occurrence of signs on x-ray that suggest the cephalomedullary nail is not functioning properly, average hip range of motion, mobility, independence, and pain at 3 months, 6 months, 1 year and 2 years after surgery.

REFERENCES

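### Outcomes with a 'no difference' hypothesis should be judged from 95% confidence intervals, not from non-significant tests, and the 1-year and 2-year follow-up statements need reconciling (primary TAD analysis unaffected)

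*Combined protocol and SAP*

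**What the plan says.** Under Statistical Procedures, "The Student t-test and the Fisher's exact test will be used to compare outcomes between the two cohorts". The Scientific Abstract repeats this ("Student t-test and Fisher's exact test will be used to compare outcomes between the two cohorts"), and no other analysis method is given for outcomes.

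The Research Question(s)/Hypothesis(es) paragraph expects an improvement in TAD, fluoroscopy use and K wire passes. For several other outcomes it expects the arms to be alike: lag-screw position, operative time, blood loss, and radiographic cut-out at each visit. (Blood loss has a hypothesis here but is not in the outcome lists.) On function and pain it says "Additionally, we expect no difference in hip range of motion", and goes on to "mobility and social dependency as defined by the Harris Hip Score, or pain level at any of the follow up visit time points". It gives no margin and does not say how the absence of a difference will be judged.

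On timing, the purpose paragraph in Background says that "1 year follow-up will compare postoperative complications, mobility, range of motion, social dependency and pain level between procedures". The Study Design paragraph, which follows directly, says that cut-out, range of motion, Harris Hip Score and pain "will be assessed at 3 month, 6 month, 1 year, and 2 year follow up visits". The Scientific Abstract lists the same four visits, and the lay abstract refers to "average hip range of motion, mobility, independence, and pain at 3 months, 6 months, 1 year and 2 years after surgery".

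**The concern.** A t-test or Fisher's exact test is built to detect a difference. When the hypothesis is that there is none, a p-value above 0.05 is the expected result both when the arms are alike and, in a small trial, when they differ by a moderate amount. The plan gives nothing else to base a conclusion on. A report written from it could present a row of non-significant results as confirming the hypothesis, although the data might be compatible with a difference that matters to patients.

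These outcomes are more than incidental. Function and pain are in the stated purpose, and their absence from the previous study is part of the argument for doing this one. Operative time and lag-screw position are designated secondary outcomes.

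The conflict over follow-up length decides whether three or four visits enter the comparison of function and pain.

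**Working it through.** **Plan's own figure first.** Inputs from Statistical Procedures: difference 8 mm, SDs 6.68 and 6.30 mm, alpha 0.05, power 0.80. Two-sided testing is assumed, as the plan does not say.

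- Root-mean-square SD = sqrt((6.68² + 6.30²)/2) = 6.49 mm.
- n = 2 × (1.96 + 0.84)² × 6.49² / 8² = 10.3, so 11 per cohort. This matches the plan. The noncentral t gives 11.4, so 12.
- Power for TAD at the planned 30 per cohort is above 99%. The primary analysis is secure.

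**Continuous outcomes with a no-difference hypothesis, 30 per arm, one visit, complete data.**

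- 95% CI half-width = t(0.975, 58 df) × sqrt(2/30) = 2.002 × 0.258 = 0.52 SD. For scale only: with an assumed Harris SD of 10, 15 or 20 points, this is 5.2, 7.8 or 10.3 points.
- Difference detectable with 80% power (noncentral t): 0.74 SD.
- True difference 0.5 SD: noncentrality 0.5 × sqrt(30/2) = 1.94, power 48%, so p>0.05 in 52% of trials.
- True difference 0.3 SD: noncentrality 0.3 × sqrt(30/2) = 1.16, power 21%, so p>0.05 in 79% of trials.
- With assumed losses of 20% and 40% (24 and 18 per arm), the half-width grows to 0.58 and 0.68 SD.

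**Can the interval show no difference?** Suppose the true difference is zero. The chance that a single-visit 95% CI lies wholly inside a margin depends strongly on that margin: 4% for ±0.5 SD and 72% for ±0.8 SD. For an 80% chance the margin must be about 0.84 SD, from (1.96 + 1.28) × 0.258 (normal approximation).

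**Cut-out.** Background gives an incidence of nearly 8%. If the true rates were 8% and 2% (the 2% is assumed), Fisher's exact test at 30 per arm would have about 2% power. With 2 of 30 events in each arm, the 95% CI for the difference (Newcombe) is −15 to +15 percentage points. The documents give no proportion for lag-screw position, so no figure is offered there.

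**Averaging over visits.** With an equal within-patient correlation rho between visits, the variance ratio of a four-visit mean is (1 + 3 × rho)/4.

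| Assumed rho | Ratio | Half-width = 0.517 × sqrt(ratio) |
|---|---|---|
| 0.5 | 0.625 | 0.41 SD |
| 0.8 | 0.85 | 0.48 SD |

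The gain is modest and has a price. A 0.74 SD difference confined to one visit becomes 0.74/4 = 0.18 SD in the average. It is then detected with 12–14% power, against 80% by that visit's own t-test.

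**Follow-up.** Set side by side, one purpose sentence refers to 1 year, while Study Design and both abstracts list visits to 2 years. The documents do not say whether the purpose sentence sets the end of follow-up, names a comparison point, or is left over from another plan.

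**The case against.** The strongest reply is that expecting no difference is a forecast and not an equivalence claim. Nowhere do the documents say that p>0.05 will be taken as proof, and a reader who infers that the sponsor intends to declare equivalence goes beyond the text. That stands. The point is only that the stated tests give no sound basis for the conclusion the hypothesis anticipates.

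It can also be said that function and pain form a third, unpowered tier, introduced after the primary and secondary outcomes. That limits the importance of the point but does not remove it, since operative time and lag-screw position are designated secondary outcomes.

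Four stronger readings are tempting, and the documents do not support them:

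- **Multiplicity as the main fault.** One t-test per scale per visit (about 12) is an inference from silence. A chance finding would also contradict the hypothesis rather than favour it.
- **A required key scale with one averaged contrast.** The hypothesis concerns every visit. An average answers a different question and can hide a difference at one visit.
- **Near-impossibility of showing no difference.** That holds only for a narrow margin such as ±0.5 SD, which is smaller than the half-width itself. The documents give no margin, so no single success rate can be attached to the plan.
- **Serious bias from dropout or death.** The documents give no loss rate, mechanism or correlation. Large biases need a mechanism acting in one arm only, and blinding of patients makes that less likely.

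**Conclusion.** The point holds as a cheap improvement to the secondary and additional outcomes; the TAD analysis and its sample size stand. With 30 per arm, a non-significant result leaves differences of about half an SD or more open, and it occurs in 52% of trials with a true 0.5 SD difference. A conclusion of no difference drawn from the named tests alone would be unsound.

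The figures assume two-sided testing at 0.05, complete data, roughly normal scores and a common SD. Losses widen the intervals. Because the documents give no SDs for these outcomes, the clinical meaning of 0.52 SD cannot be settled from them.

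The follow-up conflict is real and lies within the Background section itself, though the weight of the text is on 2 years. A reader might infer that 1 year is the designated comparison point. The documents do not say so, and the sponsor must settle it.

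**What to change.** Add a short passage to Statistical Procedures:

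1. For every outcome with a no-difference hypothesis (range of motion, Harris Hip Score, pain, cut-out, lag-screw position, operative time, blood loss), report the arm difference with its 95% CI. For follow-up outcomes, do so at every visit.
2. State that conclusions rest on what the interval excludes and not on p>0.05.
3. Claim no difference only where the interval lies inside a largest unimportant difference that the investigators state before seeing the data. Where none is stated, or the interval crosses it, report the result as an estimate.
4. Optionally, and as supportive only, add a repeated-measures model on all observed visits, or a t-test on each patient's mean over available visits. Neither replaces the visit-specific estimates.
5. Make the purpose paragraph and the Study Design paragraph give the same follow-up.

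The cost is a few sentences, with no new patients, visits or data. There are two downsides. A margin needs clinical input that the documents do not contain. And at this sample size the functional results will mostly read as inconclusive rather than as no difference.
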